1.4 INSTITUTIONAL REVIEW BOARDS

Fred Hutchinson Cancer Research Center Institutional Review Board
Institutional Review Office
[name]
Seattle, WA 98109-1024
[contact]
e-mail address: [contact]

Comité Institucional de Bioética
Asociación Civil Impacta Salud y Educación
[contact] [name]
e-mail address: [contact]

SIGNATURE PAGE

**Modulating the Impact of Critical Events in Early HIV Infection: Effect of ART Initiation
and Alcohol use**

Sponsored by:

National Institute on Drug Abuse (NIDA)
U. S. National Institutes of Health (NIH)

I, the Principal Investigator, agree to conduct this study in full accordance with the provisions of this protocol. I will comply with all requirements regarding the obligations of investigators. I also agree to maintain all study documentation for at least two years.

I have read and understand the information in the Investigator's Brochures and/or package inserts, including the potential risks and side effects of the products under investigation, and will ensure that all associates, colleagues, and employees assisting in the conduct of the study are informed about the obligations incurred by their contribution to the study.

[name], PhD, MPH
Principal Investigator and Protocol Chair

Signature of Principal Investigator

Date

EXECUTIVE SUMMARY

Protocol Title: Modulating the Impact of Critical Events in Early HIV Infection: Effect of ART Initiation and Alcohol use

Short Protocol Title: The MERLIN Study

Sites: IMPACTA San Miguel and Barranco Clinical Research Sites at IMPACTA PERU Clinical Trials Unit in Lima, Peru.

Planned Starting Date: January 2017

Planned Ending Date: December 2022

Study Rationale: This study will investigate the relative long-term benefit of early initiation of antiretroviral therapy (ART) in men who have sex with men (MSM) and transgender women (TW) with recently-acquired HIV infection. The impact of early ART initiation will be assessed in participants according to their Fiebig stage at diagnosis. Fiebig staging uses the presence of HIV RNA, p24 and patterns of antibodies bands seen on western blots to define 5 stages during the first 3-4 months after HIV acquisition plus a 6th stage for long-term infection.

The overall objective is to determine the impact of time of ART initiation and high-level alcohol use on a number of HIV-related clinical parameters. These include time to viral suppression, CD4 count, HIV reservoir, changes in the gut microbiome and neurocognitive functioning.

Primary Objectives:

- 1) To determine the relative long-term benefits of immediate vs. early vs. delayed (by 6 months) initiation of ART.
- 2) To determine the impact of high-level alcohol use on the relative long-term benefits of immediate vs. early vs. delayed ART initiation

Primary Endpoints (1):

- 1) Measure the impact of early treatment on cell-activation, and inflammation by comparing cellular markers of inflammation in study participants who initiated treatment at varying times after HIV acquisition.
- 2) Measure the impact of early treatment on the replication-competent HIV reservoir (size of the reservoir and types of cells involved) in study participants who initiated treatment at varying times after HIV acquisition.
- 3) Determine whether early ART initiation prevents long-term changes in gastrointestinal tract bacterial microbiota and correlate these changes with systemic markers of inflammation and disease progression such as the activity of the kynureine pathway of tryptophan catabolism and plasma concentrations of the inflammatory cytokine interleukin-6 (IL-6).

- 4) Document the impact of early ART initiation on 'non-HIV-associated' diseases such as neurocognitive disorders. Assess the correlation of these clinical outcomes with laboratory markers of cell activation, inflammation and HIV reservoir size and characteristics.
- 5) Determine the impact of high-level alcohol use on the outcomes listed in 1-4, after controlling for time of ART initiation.

Primary Endpoints (2):

- 1) Examine the time course of seeding of the replication-competent HIV reservoir quantifying the size of the reservoir and identifying the types of cells involved at time-points close to HIV acquisition.
- 2) Characterize innate immune responses (cytokines and other soluble mediators) shortly after infection and determine the impact of these responses on the strength and character of the subsequent adaptive immune response to HIV, as well as the size and characteristics of the HIV reservoir (see above).
- 3) Probe changes in gastrointestinal tract bacterial microbiota shortly after HIV infection and determine the correlation of these changes with two established markers of disease progression: the activity of the kynurenine pathway of tryptophan catabolism and plasma concentrations of the inflammatory cytokine interleukin-6 (IL-6).

Design: The MERLIN Study extends the follow-up of participants enrolled in the SABES Study, a study of ~250 MSM and TW in Lima with acute and recent HIV infection enrolled in an early vs. deferred antiretroviral treatment study. The MERLIN study will offer follow-up to all of the patients enrolled in the SABES study, prioritizing the participants who also were enrolled in a related Observational Study, in which baseline peripheral blood mononuclear cell (PBMC) isolation sampling was conducted. Additionally to the participants previously enrolled in SABES, up to 25 additional participants with acute HIV diagnosis will be enrolled directly in this study and will be treated immediately upon diagnosis.

Consenting eighteen-year old or older MSM and TW, who participated and received ART in the SABES Study and who have acceptable hematologic, liver, and renal function will be considered to participate in the MERLIN study, in which they will continue a 3-drug ART regimen.

Because of the low number of participants, which acute infection who received immediate treatment in the SABES study and who could be eligible for MERLIN, a new enrollment and follow-up cohort will be open with up to 25 participants (see above). In this cohort, participants with acute HIV infection will initiate antiretroviral treatment immediately after receiving diagnosis and will also be followed up for an extended time.

Duration: Up to 5 years from enrollment on this protocol (through 2022) with visits timed referencing date of HIV diagnosis and original SABES study visits (or SABES enrollment if applicable).

Treatment Regimen:

In *SABES* Step 3, participants had been randomized to either one of the following arms: Immediate Arm: to immediately receive ART for 48 weeks; or Deferred Arm: to delay treatment for 24 weeks (unless Peruvian criteria for initiation of treatment are met), and then receive ART at 24 weeks.

For the purposes of correlative studies, participants in the Immediate Arm are further categorized as initiating Immediate ART (in Acute HIV: Fiebig I/II) or Early ART (Recent HIV: Fiebig III/V) infection.

The MERLIN participants will initiate the co-formulation EVG/COBI/FTC/TDF (Genvoya) for its component TAF.

EVG/COBI/FTC/TDF is not readily available in private or public sector HIV care in Peru, but it is considered acceptable based on FDA-approval and US-based HIV guidelines to the Peruvian Ministry of Health (MOH).

Participants receiving protease-inhibitor (PI)-based regimens at MERLIN enrollment will be transitioned to Genvoya after individual evaluation.

- **Group A:** This group will be comprised of persons who initiated EFV/FTC/TDF during *SABES* Step 3.

These participants will continue with EVG/COBI/FTC/TAF.

- **Group B:** This group will be comprised of persons who initiated EFV/FTC/TDF during *SABES* Step 3 and completed all 48 weeks of the protocol before MERLIN (or the Observational Study) began enrollment.

These participants were transferred to continue their in the MOH/TARGA (Peruvian Government) HIV clinics and received non-study first-line ART (EFV + lamivudine (3TC) + zidovudine (AZT), or other regimen) after completing *SABES* Step 3 and up to their enrollment in the MERLIN study.

These participants will continue treatment with EVG/COBI/FTC/TAF.

- **Group C:** This group will be comprised of persons who initiated EVG/COBI/FTC/TDF during *SABES* Step 3 or other persons currently taking a PI or INSTI-based regimens. Because INSTI-based regimens are considered preferential as described above, at MERLIN enrollment, these participants will be transferred to EVG/COBI/FTC/TAF. Persons who require to take PI-based regimens have generally had EFV intolerance/hypersensitivity or even virologic resistance. For these reasons, they cannot receive other treatments. All persons receiving PI-based regimens will also be transitioned to EVG/COBI/FTC/TAF unless a clinical contraindication exists.

- **Group D:** This group will consist of participants who were diagnosed with acute infection

and enrolled in MERLIN immediately after their diagnosis and who will initiate antiretroviral treatment immediately with EVF/COV/FTC/TAF.

Evaluations: All participants will be evaluated at regular intervals for primary and secondary outcomes.

BACKGROUND

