changes, and decrease seeding of the reservoir. Initiation of ART in FI-II will have the greatest benefit. CD4 counts and peripheral inflammatory markers in the FIII-V group and the group treated at 24 weeks will approach those in the FI-II group at 1.5 and 3.5 years after ART initiation; in contrast, changes in the GI microbiome and the HIV reservoir over time will be more modest. 2. Irrespective of the time of ART initiation, alcohol use will compound the negative effects of HIV to generate greater levels of dysbiosis, microbial translocation, up-regulation of inflammatory pathways, and seeding of the HIV reservoir.

Specimens from the *SABES* and *MERLIN* studies will be used for a series of laboratory investigations probing the mechanisms by which early treatment reduces the HIV reservoir and HIV-associated inflammation, and seeking to determine how soon after HIV acquisition ART must be initiated to confer these beneficial effects. The most in-depth studies will prioritize participants enrolled during the latter half of the *SABES* study who had large PMBC collections at the time of HIV diagnosis and throughout follow-up. These include the following 3 groups based on time of ART initiation: a) *Immediate*: during FI-II (N~20), b) *Early*: during FIII-V (N~35) or c) *Deferred*: at 24 weeks after diagnosis (N~55). A small number of additional studies may be conducted on all participants in the *SABES* study: a) *Immediate*: during FI-II (N~35), b) *Early*: during FIII-V (N~72) or c) *Deferred*: at 24 weeks after diagnosis (N~115). The *MERLIN* study will assess outcomes after 1.5 and 3.5 years after initiation of ART in these MSM and TGW. The results will be evaluated every 6 months during the follow-up of the participants in the study (up to the end of 2022). Laboratory analyses will be conducted in Lima, Perú and Seattle, WA as well as in the laboratories of our collaborators at University of California, San Francisco (UCSF) and University of Montreal (UoM). Additional neuropsychiatric and biologic data will be collected to evaluate neuroinflammation and cognitive changes in early HIV infection (collaborators at UCSF, Yale, and UNC).

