4.3 PROBLEM UNDER INVESTIGATION

Results of several recent studies suggest that initiation of ART soon after HIV infection can reduce HIV-induced inflammatory changes and seeding of the reservoir. Clinical studies also suggest that early initiation of therapy can have a beneficial impact by reducing the HIV-associated morbidity that persists even when HIV replication is successfully achieved through ART. These studies leave open the question of how soon after HIV acquisition ART must be initiated to achieve these beneficial results. While initiation of ART during hyper-acute (Fiebig stages I and II) might seem optimal, detecting such individuals and linking them rapidly to care poses huge logistical challenges, not the least of which is instituting more wide spread screening for HIV infection using NAAT (nucleic acid amplification test). The intent of this study is to determine the impact of early treatment initiation among patients with acute (HIV RNA+/ seronegative) or very recent (HIV seropositive with a documented HIV RNA tested within the past 3 months) HIV infection. Most participants in this study participated in the SABES study (see below) and initiated ART early after HIV acquisition. Because participants were randomized to start ART at different times, the proposed studies will allow assessment of the relative impact of ART initiated at various times during the first year of infection. In addition, a small number of participants with chronic HIV infection and a small number of HIV-uninfected participants will be enrolled for comparison.

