5. HYPOTHESIS

ART initiation during FI-II stages will largely prevent changes in GI microbiota and inflammatory markers, and reduce the size of the reservoir of replication-competent HIV.

- 1) Over time CD4 counts and peripheral inflammatory markers in seropositive participants who initiate ART 2 to 8 months after infection (ie in the Early and Deferred Arms) will approach those who initiated ART during Acute (FI-II) HIV; in contrast, we expect that these individuals initiating ART subsequent to acute infection will demonstrate persistent changes in the GI microbiome and in the HIV reservoir.
- 2) High-level alcohol use will compound the negative effects of HIV to generate greater levels of dysbiosis, microbial translocation, and up-regulation of inflammatory pathways, leading to increased seeding of the HIV reservoir prior to ART initiation. Early treatment should diminish, but not completely prevent, the changes in the microbiome associated with alcohol consumption and their impact on immune activation and seeding of the HIV reservoir.

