6.1 PRIMARY OBJECTIVES

- 1) To determine the relative long-term benefits of immediate vs. early vs. deferred initiation of ART.

Initiation of ART during Fiebig I-II, while theoretically appealing, is currently infeasible in clinical practice because the duration of FI-II is very short (10 days) and because antibody-based tests, used almost world-wide, are unable to diagnose FI-II. Six months of ART initiated shortly after seroconversion (FIII) can improve many immune parameters, although not to the near normal level seen when ART is initiated during FI-II [3]. Longer-term follow-up of seropositive participants who started ART ~2-8 months after HIV acquisition compared to those initiating ART during FI-II is needed to see whether markers of inflammation and residual viral load might continue to improve after 6 months, decreasing the difference between the groups. Methods: We will evaluate the 3 groups using specimens from equivalent times after ART initiation through the first 5 years of ART usage, comparing CD4 counts, time to undetectable VL, GI microbiota, and inflammatory markers. The size of the replication-competent HIV reservoir in PBMCs will be compared using measurements of multiply spliced viral RNA (msRNA) and the degree of low-level infection of new cells by assessing the production of circular viral DNA (2LTR HIV DNA). We will model the size and persistence of the viral reservoir across all ART-adherent study participants. In a subset of individuals from each group, the proviral integration sites will

be defined at ART initiation and after 1.5 and 3.5 years to assess the maintenance of the reservoir by proliferating CD4 cells. We will continue evaluating endpoints annually or biannually, as long as participants remain on study.

- 2) To determine the impact of high-level alcohol use on the relative long-term benefits of immediate vs. early vs. delayed ART initiation

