7.1 GENERAL STUDY DESIGN

This protocol for the MERLIN study describes the extended follow-up of participants enrolled in the *SABES* study, a study of ~250 HIV+ MSM and TGW in Lima, Perú. In this study, we will enroll up to 25 individuals with acute HIV infection.

The *SABES* study: The ongoing *SABES* study combines laboratory and epidemiologic data with

modeling to investigate the hypothesis that early ART initiation and management of alcohol use disorder will prevent onward HIV transmission among MSM/TGW diagnosed with acute (FI-FII: Ab-/HIV RNA+) or recent (≤ 3 months) HIV infection (FIII-V). The SABES study population is MSM and transgender women (TGW) not using feminizing hormones (all referred to as "MSM" from here on) in Lima. This study is being conducted in 3 phases: 1) HIV screening, 2) monthly follow-up testing of HIV-uninfected participants by point-of-care EIA and NAAT testing for HIV RNA in pools of seronegative specimens (pools are run daily), and 3) enrollment of MSM with incident HIV infection into a randomized ART treatment study (Figure 1). Only participants with acute (seronegative but HIV RNA+) or recent HIV infection (EIA+ with a prior HIV-negative test within 3 months) are eligible for enrollment in the treatment phase of the SABES study. These participants are stratified by acute vs. recent infection and randomized 1:1 to Immediate arm (to receive ART immediately) or Deferred arm (to receive ART beginning at 24 weeks or when the participant meets Peruvian treatment initiation thresholds, whichever comes first) (Figure 1). We completed enrollment of 225 HIV+ participants into the SABES study by the end of March 2016. A small number (5-10) of additional participants will be enrolled in SABES; those with symptomatic acute HIV infection will receive ART immediately, in accordance with current Peruvian treatment guidelines and will therefore not be randomized to possibly delay ART. The Human Subjects section contains a discussion of risks and benefits. All SABES participants received either EFV/FTC/TDF or EVG/COBI/FTC/TDF as first line medication. Virologic suppression at 48 and 96 weeks is equivalent for both regimens when used as initial treatment [48]; however because EVG/COBI/FTC/TDF may result in more rapid viral suppression we began using EVG/COBI/FTC/TDF for new participants when it became available as a donated drug in late 2015.

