14. STATISTICAL CONSIDERATIONS

14.1. PRIMARY OBJECTIVES

- 1) To determine the relative long-term benefits of immediate vs. early vs. delayed initiation of ART.
- 2) To determine the impact of high-level alcohol use on the relative long-term benefits of immediate vs. early vs. delayed ART initiation

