14.6.5 DNA INTEGRATION SITES

Drs. [name] and [name] will characterize and compare the HIV DNA integration sites in subjects with and without high-level alcohol use who started ART in Fiebig stages I-II, III-V and in the deferred ART arm. Among participants with sustained suppression of HIV RNA to undetectable levels, a total of 45 participants (~15 subjects from each group) will be studied upon enrollment (prior to the initiation of ART), and after 3.5 years of ART. PBMC from the subset of participants agreeing to leukapheresis will be preferentially selected for these studies.

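### Only the Immediate arm is split by infection stage, so both comparisons with Deferred in Primary Objective 1 mix ART timing with stage at diagnosis

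*Protocol*

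**What the plan says.** Section 7.1 describes the SABES allocation: "These participants are stratified by acute vs. recent infection and randomized 1:1 to Immediate arm" or to the Deferred arm. Both stages are therefore expected in both arms.

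The Executive Summary (Treatment Regimen) then applies the stage split to one arm only: "For the purposes of correlative studies, participants in the Immediate Arm are further categorized as initiating Immediate ART (in Acute HIV: Fiebig I/II". The remainder of that arm, with recent infection (Fiebig III-V), is called Early. No matching split is given for Deferred.

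The asymmetric groups recur through the protocol:

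- Section 4.1 lists Immediate (about 35), Early (about 72) and a single Deferred group, "at 24 weeks after diagnosis (N~115". For the in-depth studies the sizes are about 20, 35 and 55.
- Section 5 refers to "seropositive participants who initiate ART 2 to 8 months after infection (ie in the Early and Deferred Arms", again with Deferred as one block.
- Section 6.1, in the methods under Primary Objective 1: "We will evaluate the 3 groups using specimens from equivalent times after ART initiation through the first 5 years of ART usage".
- Section 14.1: "To determine the relative long-term benefits of immediate vs. early vs. delayed initiation of ART".
- Section 14.6.5 compares integration sites in those "who started ART in Fiebig stages I-II, III-V and in the deferred ART arm".

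Section 4.3 rests the timing question on the allocation: "Because participants were randomized to start ART at different times, the proposed studies will allow assessment of the relative impact of ART" begun at various points in the first year. The study rationale in the Executive Summary says that impact will be assessed by Fiebig stage at diagnosis, but no section applies this to Deferred.

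**The concern.** Randomisation within strata protects two kinds of comparison: the whole Immediate arm against the whole Deferred arm, and the two arms within a stratum. Comparing one stratum of the Immediate arm with both strata of the Deferred arm is neither. People diagnosed while seronegative may differ from people diagnosed after seroconversion for reasons unrelated to when ART began, such as how they came to be detected. In the two comparisons with Deferred, any such difference would be read as an effect of ART timing.

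The split is introduced for correlative studies, but Sections 6.1 and 14.1 carry the same groups into a primary objective. The fault lies in the group definition that the protocol fixes, not in a model still to be specified, so an analysis plan that follows these groups inherits it. Section 4.3 also does not distinguish the randomised comparison (immediate versus deferred) from the observational one (Immediate versus Early).

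**Working it through.** The protocol gives no effect size, alpha or power for these comparisons, so there is no stated figure to reproduce. Two-sided 5% tests and 80% power are assumed below.

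**Inputs.** Group sizes from Section 4.1: 35 / 72 / 115 for all SABES participants and 20 / 35 / 55 for the in-depth set. Allocation from Section 7.1: 1:1, stratified by acute versus recent.

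**Consistency.** 35 + 72 = 107 against 115, and 20 + 35 = 55 against 55, as 1:1 allocation would give. The total, 107 + 115 = 222, is close to the 225 enrolled according to Section 7.1.

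**Implied acute share of Deferred.** p = 35/107 = 0.327, and 115 × 0.327 = 37.6, so about 38 acute and 77 recent. In-depth set: 20/55 = 0.364, so about 20 acute and 35 recent.

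**Bias.** Let d be the acute-minus-recent difference in an outcome, in SD units, with no timing effect.

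- Immediate minus Deferred: (1 − p)d = 0.673d
- Early minus Deferred: −p·d = −0.327d
- Whole Immediate arm minus Deferred: (35/107 − p)d = 0

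**False-positive rates.** The documents do not give d, so a range is shown. Rates come from simulation (40,000 replicates, unit SD, pooled t-tests, 38 acute of 115 in Deferred; 20 of 55 in the in-depth set).

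| Assumed d (SD) | Immediate−Deferred: bias | Rate | In-depth rate | Early−Deferred: bias | Rate | In-depth rate |
|---|---|---|---|---|---|---|
| 0.3 | 0.20 | 18% | 11% | −0.10 | 10% | 8% |
| 0.5 | 0.34 | 39% | 21% | −0.16 | 19% | 12% |
| 0.8 | 0.54 | 76% | 44% | −0.26 | 38% | 24% |

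A normal approximation with SE = sqrt(1/n + [1 + p(1 − p)d²]/115) agrees. At d = 0.5 for Immediate versus Deferred, SE = sqrt(1/35 + 1.055/115) = 0.194 and 0.336/0.194 = 1.73, giving about 41%. The same formula gives 19% for Early versus Deferred.

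**Sensitivity at d = 0.5.**

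- If Deferred were 25% or 40% acute, the rates would be 48% or 33% (Immediate−Deferred) and 12% or 25% (Early−Deferred).
- If 10 of the 35 Immediate participants were non-randomised acute cases, p = 25/97 = 0.258 and Immediate−Deferred carries 0.742d.
- If all 25 Group D participants joined Immediate (60 against 115), the approximation gives 55% for Immediate−Deferred.

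**After splitting Deferred.** In the main-set simulation, within-stratum and stratum-adjusted tests reject 4.8% to 5.1% of the time. This does not model selection into MERLIN.

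**Precision**, SE = sqrt(1/n1 + 1/n2), with the 80%-power difference = 2.80 × SE:

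| Comparison | Sizes | SE (SD) | Detectable (SD) |
|---|---|---|---|
| Immediate vs all Deferred | 35 v 115 | 0.193 | 0.54 |
| Immediate vs acute Deferred | 35 v 38 | 0.234 | 0.66 |
| Early vs all Deferred | 72 v 115 | 0.150 | 0.42 |
| Early vs recent Deferred | 72 v 77 | 0.164 | 0.46 |
| Acute contrast, in-depth set | 20 v 20 | 0.316 | 0.89 |

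The inverse-variance pooled arm effect has SE = 1/sqrt(1/(1/35 + 1/38) + 1/(1/72 + 1/77)) = 0.134. Unstratified 107 versus 115 also gives sqrt(1/107 + 1/115) = 0.134.

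**The case against.** The strongest reply is that the groups are defined by stage when ART starts, not at diagnosis. The endpoints concern time from HIV acquisition to treatment, and by 24 weeks after diagnosis nearly all Deferred participants are past Fiebig V whatever their stage at diagnosis. On that view stage in the Immediate arm is the exposure. This holds for Immediate versus Early, which should be kept. It does not rescue the mixed comparator. On that time scale Deferred still pools people starting 24 weeks after a seronegative diagnosis with people whose infection may already have been up to three months old at diagnosis, and any selection linked to being caught in the acute stage remains.

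The second reply is that the rates depend on a lasting stage effect, independent of timing, that no section documents; monthly testing may make it small. This stands: the rates are illustrative. The imbalance in acute share does not depend on them.

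Third, an analysis plan could adjust for the stratum, and the protocol mentions both Fiebig stage at diagnosis and duration of infection before ART as things to be used. That makes the fault repairable, but it does not change the group definitions. Section 4.3 also never says outright that the three-group contrasts are randomised; the criticism is that it draws no distinction.

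Finally, within-stratum contrasts estimate the effect of a 24-week delay after diagnosis, which is narrower than time since infection. It is, however, the question that the randomisation can answer.

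**Conclusion.** The point holds and should be fixed. Two of the three pairwise comparisons under Primary Objective 1 set a group of one stage against a mixed group: 100% versus about 33% acute, and 0% versus about 33% acute. They therefore carry about 67% and 33%, in opposite directions, of any stage difference unrelated to timing.

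This rests on one inference, that stratified 1:1 allocation gives Deferred about the same acute share as the Immediate arm. The false-positive rates rest in addition on assumed stage effects of 0.3 to 0.8 SD, two-sided 5% tests and no stratum adjustment.

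Comparing within strata removes this source of bias but does not make the contrasts fully randomised. Section 8.1.1 selects participants after randomisation, by last viral load below 1000 copies/mL, uninterrupted ART and new consent.

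**What to change.** 1. Split Deferred by the randomisation stratum. For comparisons with Deferred, use Acute-Immediate versus Acute-Deferred, Recent-Immediate versus Recent-Deferred, and a stratum-adjusted overall arm effect. Carry these definitions through Sections 4.1, 5, 6.1, 14.1 and 14.6.5.
2. Keep Immediate (FI-II) versus Early (FIII-V), labelled as observational.
3. State that Group D, and any late SABES enrolees with symptomatic acute infection who were not randomised, stay out of the randomisation-based contrasts and are reported as a labelled supplementary group.
4. In Section 4.3, limit the randomisation claim to immediate versus deferred. Add that even within-stratum contrasts are protected only so far as entry and retention are similar between arms, and report MERLIN entry by arm and stratum.

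The cost is wording in the protocol and analysis plan, since arm and stratum come from the SABES randomisation. The adjusted arm effect loses no precision. The acute contrast does: its detectable difference rises from 0.54 to 0.66 SD, and in the in-depth set from 0.73 SD (20 v 55, SE 0.261) to 0.89 SD. For the recent stratum the rise is from 0.42 to 0.46 SD.
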